3.3.1 Potential Risks

Risk related to study interventions

To promote additional safety related to study interventions, both study intervention arms (immediate intrapartum nipple stimulation therapy via electric breast pump versus immediate synthetic oxytocin infusion without nipple stimulation) will require continuous fetal cardiotocography during intervention use to monitor fetal heart rate patterns and contraction frequency. There will be clear recommendations in the study protocol for titration of both interventions to ensure that the frequency of contractions is within the recommended goal range. Therefore, no serious or life-threatening adverse events directly related to the study intervention are expected. To prevent the risk of nipple soreness or pain related to the incorrect use of an electric breast pump, each subject assigned to the study intervention will undergo a tutorial prior to the initiation of an electric breast pump to review correct breast pump flange fit and placement. Lanolin ointment will also be provided to subjects. The device manual or Instructions of Use will be provided to each subject to be the primary source of information of risks of the device provided by the study, should they choose to use it. The subject will also have the option to use their own home electric breast pump if they desire.

Risks related to biospecimen collection

There is a small risk associated with biospecimen collection. The risks include discomfort from the needle stick and/or IV catheter for venous blood draw, the possibility of pain or bruising at the site of the blood draw, the possibility of feeling lightheaded, and the rare risk of infection at the site of blood draw. There are no significant risks to providing mid-stream urine collection or collecting urine from an indwelling foley catheter. If the patient is having intermittent bladder catheterization, additional catheterization events will not be performed purely for study purposes.

There is minimal risk in milk collection including temporary discomfort in the breast/nipple for a short time after pumping. We anticipate that the small volume of milk (0.5ml up to twice a day) collected for the study will not affect infant growth or interfere with the nutritional needs of full-term infants.

Risk related to study interactions and subject confidentiality

There will be multiple procedures in place to minimize the risk of subject confidentiality, and will be outlined in the study protocol. Subject confidentiality will be held in strict trust by all members of the research teams. Subject medical record review will be limited to just the elements needed to complete the study. Only authorized HIPAA and GCP trained study team members will be allowed to extract research data from medical records and enter it into the *REDCap* database.

At each study site, subject records are maintained in the Epic System® EMR and all research data will be collected in and maintained in *REDCap*, an established, secure, web-based capture and management tool developed at Vanderbilt University). Any paper records (e.g. signed consent forms) will be kept in a locked cabinet within a locked office that is secured always and located on the main campus within the departmental research administrative office space at each study site to ensure confidentiality of subject data.

Data use agreements will be obtained and approved across all three institutions: Weill Cornell as the primary grant institution where the PD resides, Yale University (grant sub-award institution), and Northwestern University (grant sub-award institution).

The IRB may inspect study records at any given time. In addition, all scientific publications will refer to the subjects by study identifiers only. At no time will any of the subjects in the study be identified. Identifiable study information will be maintained for up to ten years after the research is complete. After that time, it will be destroyed or de-identified. The principal investigator will keep a link that identifies subjects to coded information, but this link will be kept secure and available only to the PIs or selected members of the research team.

All samples collected at WCM will be de-identified. A secure, access-restricted linkage key connecting study IDs to patient identifiers will be maintained solely by the local research teams. [name] lab will only receive de-identified samples and coded data labeled with the study ID, and will have no access to patient identifiers. Results generated by [name] lab will be uploaded to the WCM REDCap database using the matched study IDs provided with the samples, ensuring all data remain de-identified and participant confidentiality is maintained throughout the study.

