
In conclusion, despite excellent theoretical acceptance of nipple stimulation for labor induction from patients and providers (26), we lack robust data demonstrating its efficacy and safety. A well-designed randomized clinical trial is needed, particularly in comparison to the standardly accepted clinical alternative (exogenous oxytocin). Further, more data related to oxytocin concentrations and dose response are needed to inform our understanding of the biology of oxytocin during labor induction, especially when comparing exogenous oxytocin versus stimulation of endogenous oxytocin.

It is thought that breast stimulation induces uterine contractility by increasing the level of endogenous oxytocin hormone (15) (16). However, the exact mechanism remains unclear.

To our knowledge, only one previous published randomized clinical trial tested breast stimulation by electric breast pump (Medela, Inc) (13) which showed that the time to reach the active phase of labor was significantly reduced among women who underwent nipple stimulation compared to those who received oxytocin in the hospital setting. There was no difference in the length of labor between groups once women were in the active phase of labor or mode of delivery, but the trial included just 62 women. Reassuringly, only one of the 30 women assigned to breast stimulation requested discontinuation due to nipple soreness after 5.5 hours of intermittent stimulation. There were no serious maternal or perinatal adverse events reported in the trial.

At Yale, our research team recently completed our external pilot feasibility and acceptability randomized clinical trial (Yale IRB #2000029909, Clinicaltrials.gov NCT04756089). In this pilot trial, 24 women were randomized in a 3:1 ratio to nipple stimulation with a breast pump or exogenous oxytocin infusion. Of the 18 women randomized to breast pump stimulation, one woman withdrew due to delay of clinical care and received oxytocin (cross-over rate of 1/24 (4.2%)). Of the 6 women randomized to exogenous oxytocin infusion, one woman did not receive it due to spontaneous labor progress. All other participants followed their assigned intervention (22/24, 92%). The 17 women who performed breast pump stimulation stimulated for a median duration of 198 (IQR 125-291) minutes. There were no serious adverse events for either the mothers or their fetuses/infants.

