5.1 General Design Description

The proposed study is a multicenter, pragmatic, open label, parallel group randomized trial of nulliparas to compare the effectiveness of intrapartum nipple stimulation therapy with or without adjunctive synthetic oxytocin (intervention) versus immediate synthetic oxytocin

infusion without nipple stimulation (comparator) during labor induction. Potential subjects will be recruited from the Labor & Birth units at three study sites: Yale New Haven Hospital in New Haven, Connecticut, Weill Cornell Medicine in New York, New York and Northwestern Memorial Hospital in Chicago, Illinois. We aim to test the central hypothesis that intrapartum nipple stimulation increases spontaneous vaginal delivery, shortens labor duration, improves other patient-centered outcomes, improves breastfeeding success, and does not increase adverse neonatal and maternal outcomes. We chose a randomized controlled trial, the 'gold standard' of clinical research design, with the goal of obtaining the highest quality evidence to inform clinical practice. Randomly allocating subjects to different interventions minimizes selection bias and results in groups that are comparable with regards to important confounding variables, both measured and unmeasured. Blinding of subjects, maternity care providers, and investigators is not feasible given the intervention being studied (nipple stimulation). With the limitations of the existing data, we estimated our sample size and plan our data analysis based on two-tailed tests. This will ensure that we identify the optimal management strategy for labor induction that increases spontaneous vaginal delivery, irrespective of the direction of our findings.

We will follow the Consolidated Standards of Reporting Trials (CONSORT) guidelines wherever appropriate in the conduct and reporting of this trial. (27) We will use computer-generated random sequences to assign participants to the two interventions with stratification by study site and membrane status (intact versus ruptured). Labor management will be similar in the two groups except for use of nipple stimulation (intervention group) versus immediate synthetic oxytocin infusion without nipple stimulation (control). Analysis will follow the intention-to-treat principle.

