6.2.1 Efficacy

6.2.2 Safety/Pregnancy-related policy

The study protocol has been designed to minimize risks to subjects and their neonates including the requirement for continuous fetal monitoring during receipt of either study intervention, as well as detailed steps outlined to ensure the desired contraction frequency pattern to minimize risk of abnormal fetal heart rate patterns. All subjects who are undergoing continuous fetal monitoring are observed by labor nurses, and fetal monitoring is continuously reviewed and recorded.

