The use of amniotomy (if the subject has intact membranes) and other labor procedures will be at the discretion of each subject's responsible maternity care provider (pragmatic study) and considered standard of care. If standard of care is altered based on clinical decision making by the subject's responsible treating physician or midwife, the subject will still remain in the study as long as the subject does not withdraw her consent to continue in the study.

5. Subject Management and Follow-Up

All subjects will be monitored for progression of labor and their fetus' response to labor by their responsible treating obstetrician or midwife. Each subject will undergo individualized assessment by their treating obstetrician or midwife, and the clinical decision will be made by the treating obstetrician or midwife if or when subjects in the nipple stimulation arm will be switched to the standard of care with exogenous oxytocin administration. There can be no absolute cut-offs for time or contraction responses since standard of care dictates individualized assessments for labor progression and fetal response; each birth experience is unique. Subjects in both arms of the trial should be allowed adequate time to labor before considering the induction "failed" and proceeding to cesarean section. An induction will be considered "failed" after at least 24 hours of exogenous oxytocin administration has failed to generate regular (e.g., every 3 minutes) contractions and cervical change, as is considered standard of care (36). Additionally, exogenous oxytocin generally should be administered for at least 12 hours after membrane rupture before considering the induction to have failed as is considered standard of care. (37). The time devoted to cervical ripening and/or nipple stimulation will not be included when calculating the length of induction for diagnosing failed induction.

It is expected that the fetal heart rate and uterine activity will be monitored continuously during labor and that subjects will stay in the hospital until delivery once the induction is started as is considered standard of care. Aside from the interventions described above, labor and delivery management decisions will be left to the discretion of the subject's responsible maternity care provider as is considered standard of care.

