6.4.3.3 Safety/Pregnancy-related policy

The study PD/PI ([name]) will be informed of and review any potential Adverse Events. The DSMB will review all Adverse Event Reports and other interim safety data and will provide a report to the local IRB in compliance with local standards. If a participant develops a serious adverse event, the safety of continuing the intervention will be ascertained by the participant's obstetric care provider in collaboration with the site PI.

Maternal and perinatal morbidity outcomes are pre-specified secondary outcomes and will be statistically compared between intervention groups to assess for any signal of safety concerns.

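### The safety rationale cites titration steps for both arms that the stimulation-arm text shown does not contain, and excessive contractions, fetal heart rate abnormality and nipple soreness are not listed outcomes for the by-arm safety comparison

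*Protocol*

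**What the plan says.** **Safety statements.** Section 3.3.1 of the protocol says: "There will be clear recommendations in the study protocol for titration of both interventions to ensure that the frequency of contractions" stays within the recommended range. It continues: "Therefore, no serious or life-threatening adverse events directly related to the study intervention are expected". Section 7.12 makes the same statement about titration of both interventions and draws the same inference. Section 6.2.2 refers to "detailed steps outlined to ensure the desired contraction frequency pattern to minimize risk of abnormal fetal heart rate patterns", without saying which arm the steps cover.

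**Moving to oxytocin.** Section 6.3, item 5, leaves it to the treating clinician if or when "subjects in the nipple stimulation arm will be switched to the standard of care with exogenous oxytocin administration", and adds: "There can be no absolute cut-offs for time or contraction responses". Section 5.1 describes the experimental strategy as stimulation "with or without adjunctive synthetic oxytocin (intervention").

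**Safety comparison.** Section 6.4.3.3 says the pre-specified maternal and perinatal morbidity outcomes "will be statistically compared between intervention groups to assess for any signal of safety concerns". Under Section 6.2, chart abstraction follows the outcome definitions listed in the protocol.

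**Prior experience.** Section 2.1 reports, from the one earlier randomised trial of an electric pump, that "only one of the 30 women assigned to breast stimulation requested discontinuation due to nipple soreness after 5.5 hours" of intermittent stimulation.

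**The concern.** There are two linked problems.

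First, the inference that no serious events are expected rests partly on titration guidance said to be in this protocol. If the guidance is missing for the experimental arm, ethics and monitoring boards are reading a rationale that the procedures do not support. Section 7.12 itself says that the risks of stimulation are not viewed as minimal because data on its use are limited, so the accuracy of that rationale matters.

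Second, continuous cardiotocography is required in both arms to watch contraction frequency and fetal heart rate, yet neither appears as an outcome. The trial could report no difference in safety without having compared, on a common definition, the events that this monitoring is meant to detect. In an open-label trial, general adverse event reports may not be recorded to the same standard in the two arms.

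**Working it through.** **1. Titration steps by arm, in the text shown.**

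| Element | Oxytocin arm | Stimulation arm |
|---|---|---|
| Starting level and step interval | Given (6.3, item 3) | Not given |
| Upper limit | Given (6.3, item 3) | Not given |
| Adjustment to contractions | Rate changes depend on fetal status, contraction status and coping; restart rule mentions tachysystole (6.3, item 3) | Not given |
| Stopping | Stop and restart text (6.3, item 3) | Provider discretion; usual care, including stopping, for fetal heart rate abnormality (6.1.3) |
| Other | Continuous monitoring | Continuous monitoring (3.3.1), setting, pump or hand, tutorial, handouts (6.1.1; 6.3, item 3) |

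The goal range cited in 3.3.1 and 7.12 is not stated for either arm. Section 6.1.3 gives the stimulation arm a stop response, not titration by contraction frequency.

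**2. Outcomes set against the events being watched.**

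| Event | Where the protocol raises it | Listed in 5.2.2? | Nearest listed outcome |
|---|---|---|---|
| Tachysystole | Defined in 5.3.2 as an exclusion | No | Indication for cesarean or operative vaginal delivery |
| Fetal heart rate abnormality | 3.3.1, 5.3.2, 6.1.3 | No | Delivery indication, cord gases, Apgar, NICU admission, neonatal composite |
| Nipple soreness or pain | 3.3.1, 2.1 | No | Lactational mastitis; the pain scale concerns labor pain |

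**3. What the trial could estimate.** The protocol has no figure on this point to reproduce.

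- *Inputs:* 494 women per arm (Section 6.4.2). The event rate p is assumed to be 5% to 15%, because the protocol gives none.
- *Formula:* approximate 95% half-width of the arm difference = 1.96 × √(2p(1 − p)/494).
- p = 0.05: 1.96 × √(0.095/494) = 0.0272, or 2.7 percentage points.
- p = 0.15: 1.96 × √(0.255/494) = 0.0445, or 4.5 percentage points.
- With the planned 5% attrition, 494 × 0.95 ≈ 469 per arm. The half-widths become 1.96 × √(0.095/469) = 2.8 and 1.96 × √(0.255/469) = 4.6 points.

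**4. Stopping for soreness.** The earlier trial's proportion is 1/30 = 3.3%. Applied to this trial it gives 494/30 ≈ 16 women. One event in 30 is weak evidence. The exact (Clopper-Pearson) 95% interval uses beta quantiles: the 2.5% point of Beta(1, 30) is 0.08%, and the 97.5% point of Beta(2, 29) is 17.2%. Multiplied by 494, that is from under 1 to about 85 women.

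**The case against.** The strongest reply has five parts.

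*The missing steps may exist elsewhere.* In Section 6.3, item 3, the line introducing the reasons for stopping oxytocin is followed by no reasons, so text may have been lost there. Stimulation is directed by study and nursing staff, with handouts and a device manual that are not shown. This stands as a caution. But Section 3.3.1 places the recommendations in the protocol itself, and the stimulation-arm items read as complete.

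*The arm is not uncontrolled.* A reader might infer that nothing limits risk under stimulation. The protocol does not support that: monitoring is continuous, and the provider may stop stimulation at any time. What is missing is the titration that the safety statements cite.

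*The events are not necessarily unrecorded.* A reader might infer that they go unmeasured. Adverse events are collected throughout, sent to the committee chair monthly if not expedited (6.2.2.1), and reviewed for every subject, with a board meeting at least quarterly (7.12). Reasons for withdrawal are recorded (6.3.7). The data collection and adverse event appendices are not shown. All this stands. It leaves these events without a listed outcome definition for comparison by arm.

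*The statement about cut-offs is not a contradiction.* It concerns moving to oxytocin, not a response to excessive contractions.

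*The proxies measure harm directly.* Cord gases, Apgar, NICU admission and the neonatal composite do so, and may matter more to patients. But they lie downstream and do not show whether the monitored events differ between arms.

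The absence of serious events in the pilot also adds nothing here, since serious events are already collected in this trial.

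**Conclusion.** The point holds as a should-fix. Sections 3.3.1 and 7.12 claim titration guidance for both arms and rest an inference partly on it; the text shown gives it for oxytocin only. Tachysystole, fetal heart rate abnormality and nipple soreness are not listed outcomes, so the by-arm safety comparison runs on downstream proxies and general adverse event reports.

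A lesser wording conflict is whether oxytocin is added to stimulation (Synopsis, 5.1) or replaces it (6.3, item 5). That affects how events would be described by exposure.

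The gain would be an arm difference known to within about 2.7 to 4.5 points, on the assumed 5% to 15% event rate and full follow-up. The figure of about 16 women stopping for soreness is illustrative only, as it extrapolates one event.

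The conclusion assumes that no titration text was lost in extraction and that the unseen appendices do not define these outcomes. It does not show that the intervention is unsafe. Randomisation, the primary outcome and the main analysis are unaffected.

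**What to change.** 1. **Add secondary safety outcomes to Section 5.2.2.** Abstract them identically in both arms, from intervention start to delivery, using events already charted:
   - documented tachysystole, using the Section 5.3.2 definition where the chart allows;
   - documented fetal heart rate abnormality that led to the intervention being stopped or reduced;
   - nipple pain or injury that led to stopping, as descriptive data in the stimulation arm only.

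   Compare the first two by randomised arm.
2. **Reconcile Sections 3.3.1, 6.2.2 and 7.12 with 6.1.1, 6.1.3 and 6.3.** Either place the stimulation steps referred to in the protocol, or withdraw the claim and the inference that rests on it. The content of any clinical rule is for the investigators; none is proposed here.
3. **Reconcile adjunctive use of oxytocin (Synopsis, 5.1) with switching to it (6.3, item 5).**

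**Cost.** A protocol amendment and chart-abstraction time for up to 988 women, including those already enrolled. No new procedure or participant is needed. Re-reading whole-labor tracings is not required, and no section says that tracings are kept for that purpose. The price is reliance on what staff charted without blinding, which should be stated when results are reported.

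**Timing.** Last enrolment is expected in June 2026 (5.1.1). Sections 7.5 and 7.9 have identifiers deleted at the earliest opportunity after chart review, although 7.3 allows up to ten years. The fields should be added before the link to the charts is lost.

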3.3.2 Potential Benefits

There are potential direct medical benefits to individuals participating in the study if intrapartum nipple stimulation therapy via electric breast pump does shorten the duration of labor induction, reduce the risk for operative delivery and other obstetric complications, and improves lactation outcomes. Further, there are potential direct medical benefits to the newborns of individuals participating in the study if intrapartum nipple stimulation therapy via electric breast pump does improve lactation and infant feeding. Some of these outcomes, if beneficial, may also have indirect benefits on medical costs. Further, aside from potential direct medical benefits to the subjects, the subjects will know that they are contributing to the better understanding of labor induction and lactation and potentially improving to the methods used through this proposal.

4 - Study Objectives

4.1 Hypothesis

Our central hypothesis is that nipple stimulation with an electronic breast pump to induce labor increases spontaneous vaginal delivery, shortens duration of labor induction, improves patient-reported pain scores during labor, improves patient satisfaction and sense of self agency with the birthing process, and improve scores on the postpartum depression scale. We also hypothesize that participants assigned to nipple stimulation therapy during labor will be more likely to use breastfeeding as the sole source of nutrition at hospital discharge, which will be associated with improved maternal perception of milk supply, less severe newborn weight loss, and sustained breastfeeding for the recommended 6 months. Secondly, we hypothesize that intrapartum nipple stimulation will not increase fetal or neonatal morbidity outcomes. Last, by examining cost of care and health-related quality of life, we hypothesize that performing nipple stimulation therapy during labor will be more cost-effective than the comparator after considering their overall impact on labor and delivery, breastfeeding, and early infant nutrition and care in the first 6 months.

We also hypothesize that nipple stimulation therapy invokes the wide cascade of events that promote labor to a greater extent than IV oxytocin alone. We hypothesize that oxytocin in the plasma of patients performing nipple stimulation will rise less than among subjects receiving IV oxytocin at the time when the subject is first contracting regularly. We hypothesize that other proteins associated with labor (including but not limited to IL6, IL1beta, plasminogen activator inhibitor 1, C reactive protein, ICOS ligand, and ERP29 will rise more in the circulation of subjects receiving nipple stimulation therapy compared with IV oxytocin. We hypothesize that urinary metabolites of prostaglandin E2 and F2alpha will be higher in subjects receiving nipple stimulation therapy. We hypothesize that, on a systematic level, plasma changes among subjects partaking in nipple stimulation will differ from subjects receiving IV oxytocin. We hypothesize that nipple stimulation therapy will have earlier secretory activation as measured by milk sodium and conductivity) in the early days postpartum, compared to individuals receiving IV oxytocin alone.

